12 month follow-up survey. Between May 10, 2011 and March 12, 2012, we approached 974 participants for 12-month follow-up telephone survey; 272 enrolled participants were not attempted for 12-month follow-up based on their baseline or 6 month survey status. Of 974

attempted for 12-month follow-up, N=733 (75% of attempted, RS: 364, CEP: 369) completed the survey, 7 refused (RS: 4, CEP: 3), 229 were unable to contact (RS: 109, CEP: 120), and 5 deceased (RS: 3, CEP: 2).

3 year follow-up survey (extension study). Between 1/14/2014 and 10/14/2014, we attempted to contact 1004 participants for 36-month follow-up with exclusion who deceased (RS: 4, CEP: 4), who made final refusal in previous wave (RS: 22; CEP: 27), or who had no data on baseline, 6, and 12 months (RS: 84; CEP: 101). Of 1014 attempted for 36-month follow-up, 600 (600/1014=59%) participated (RS 293, CEP:307), 24 were deceased (RS:14, CEP:11), 10 refused (RS:7, CEP:3), 3 were too ill/incapable (RS:2, CEP:1), and 367 (RE:180, CEP:186) were not able to be reached.

4-year follow-up of the 3-year sample (extension study). The CPIC 4-year study was added to explore longer-term outcomes for the sample completing the 3-year follow-up, based on community stakeholder interest. In addition, this follow-up offered CPIC participants the opportunity to be participants in an additional project, the Community and Patient Partnered Research Network (CPPRN). Between 3/31/2016 and 5/26/2016, we attempted to contact 598 clients (RS: 292, CEP: 306) who completed CPIC 3 years interview participants excluding 2 that declined follow-up (RS 1, CEP 1). The telephone interview took about 15-20 minutes. At the end of the interview, a respondent was asked “Would you like to hear about the CPPRN program?” and “do you agree to be part of the CPPRN?” if answered ‘yes’. Of those, 283 (47.3%) participated (RS 143, CEP 140), with 308 not reached (RS 143, CEP 165), 1 deceased (RS 1, CEP 0), 5 refused (RS 5, CEP 0), and 1 too ill to participate (RS 0, CEP 1).⁵

A2. Weighting

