Enrollment The enrollment weight was intended to make the enrolled sample (n=1,246) representative of a specific target population.^{6,7} That target population was defined as people who were: age 18 or older, visited a participating CPIC sites during our screening window, screened positive for PHQ-8, and provided contact information. We created enrollment weights based on propensity weighting adjustment, by fitting logistic regression models to predict the enrollment among those eligible. The reciprocal of the predicted response probability was used as the enrollment weight for each participant. Five versions of the enrollment weight were created corresponding to five imputed screener data, because imputed predictors from the

screeener data were used in fitting logistic regressions. Common predictors of age, community, and type of programs were used in all models.

Attrition The analytic sample for 6 months is comprised of 1,018 participants who completed baseline, or 6-month telephone follow-up surveys. We used nonresponse weighting to address missing data for subjects who did not who did neither complete baseline nor 6 months follow-up telephone surveys. We started with a large set of independent categorical variables to be considered for a logistic regression on the outcome of response among enrolled participants. The final model included predictors that were significant ($p < 0.05$) for either intervention arm (age, gender, ethnicity, living situation, income, US born), as well as for two design variables (community and sector of the screening program). The final weights defined on the analytic sample were the product of the two adjustment factors for enrollment and nonresponse. See Supplementary Materials in publications. We applied the weights to the 36-month outcome analysis excluding 24 deceased cases (1,004 attempted - 24 deceased = 980). The weights for 3-year main analysis defined on the analytic sample were the product of the two adjustment factors for enrollment and nonresponse. See Supplementary Materials in previous publications.¹⁻³

For 4-year follow-up, we tested bivariate associations between an indicator for responding at the 4-year survey and demographic and clinical characteristics at baseline and 3 years.⁵ The weighting model to predict follow-up status from 3-year sample included screener sector, age, education, working for pay, PCS-12, poor mental health-related quality of life at baseline, and risk for homelessness at 3 years.

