Unit-Level Multiple Imputation We used a hot deck multiple imputation procedure based on an approximate Bayesian bootstrap method for unit-level missing data.^{12, 13} This model assumes that both missingness and dropout arise from mechanisms that are missing at random (MAR) in the sense defined by Rubin. Our imputation techniques attempted to include information related to the missing values whenever possible. We first modeled the propensity of response at a given time point (coded 1 if response and 0 if nonresponse). In Step 2, we stratified cases based on the quintiles of the propensity scores and used the approximate Bayesian bootstrap to select donors. In practice these procedures were applied in sequence for the baseline, 6-month, 12-month, and 3-year data, with imputations stratified by two intervention arms. We started with imputing baseline. For each of the 5 item-level imputed screener datasets, we imputed a unit-level imputation baseline dataset. Limited to the analytic sample of 1,018, we then used baseline variables as predictors for modeling 6 and 12-month follow-up data and produced unit-level imputation datasets. In modeling the logistic regression of predicting response propensities, we started with a large set of independent variables. The final baseline model included the predictors: age, gender, ethnicity, income, living situation, US born, community, and type of

screening program. The 6-month models included participants characteristics assessed at screener (age, gender, ethnicity, health insurance, and type of screening program.), and baseline clinic and service variables (multiple chronic conditions, alcohol abuse or use of illicit drugs, any depression care). The 12-month models included additional variables: community, PHQ-8 assessed at screener, mental wellness, homeless status at baseline. The 3 years models included age, gender, ethnicity, employment status, ≥ 3 chronic conditions, homeless, 12-month alcohol abuse or use of illicit drugs, no place to stay for at least two nights in the past 6 months, type of screening program, and community with additional stratum variable sector (social-community screening sector vs healthcare Screening Sector) in Step 2. Values for participants who were deceased were not imputed.

A4. Analyses

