We conducted sensitivity analyses for alternative representations of time as a continuous or class variable and for alternative weighting approaches. To investigate possible nonignorable effects, we used 2 methods. For continuous measures (such as MCS-12 and number of service visits), we multiplied ignorable-model imputations alternatively by 1.1 and 0.9 to reveal sensitivity to 10% departures from ignorable-model predictions with dichotomized versions of continuous measures (MCS-12 \leq 40) based on the imputed continuous value. For categorical imputations where reference cells were based on an underlying continuous measure (that is, predicted response propensity) including an indicator for any utilization and adjusted Bayesian bootstrap imputations reflecting unit nonresponse at a particular time point, nonignorable imputations for cases in nonboundary reference cells were generated by borrowing values from the reference cell with either the next higher or next lower value of the underlying continuous measure.¹⁹ We also conducted 12-month endpoint analysis controlling baseline with weighting adjustment and presented standardized predictions.^{2, 14}

Analyses for 3-year outcome:

We conducted 3 years endpoint analysis controlling baseline with weighting adjustment (see analysis strategy for 6 months). Given multiple secondary outcomes,¹⁹ we built on the false-discovery-rate (FDR) framework²⁰ as extended by Yekutieli and Benjamini²¹ and used both standard and FDR-adjusted p values (pFDR) in interpreting results across a large number of regression analyses. Results with pFDR $<$.05 are viewed as convincing evidence of a difference, and higher pFDR thresholds are considered as suggestive evidence. We separately calculated pFDR for the two primary outcomes, the community-prioritized outcomes, service use in the health care sector, service use in the social-community sector, medication use, and summary utilization indicators.

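### The 12-month check for non-ignorable missing data states no arm-specific departure, so its 10% scaling is a weak test of the CEP–RS difference

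*Combined protocol and SAP*

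**What the plan says.** Appendix A, A3 imputes unit-level missing data under missing at random, "with imputations stratified by two intervention arms". A4 (Analyses for 12-month outcome) then adds a check on that assumption: "To investigate possible nonignorable effects, we used 2 methods".

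- **Scaling.** For continuous measures such as MCS-12, "we multiplied ignorable-model imputations alternatively by 1.1 and 0.9", the aim being "to reveal sensitivity to 10% departures from ignorable-model predictions". The indicator MCS-12 ≤ 40 is derived from the scaled value.
- **Borrowing.** For categorical imputations, and for bootstrap imputations covering unit nonresponse, cases in non-boundary cells are re-imputed by "borrowing values from the reference cell with either the next higher or next lower value of the underlying continuous measure".

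Neither description mentions intervention arm. The 6-month and 3-year parts of A4 describe no comparable analysis.

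**The concern.** The trial estimates a contrast between arms. Missing data bias that contrast mainly when non-respondents depart from the imputation model differently in CEP and RS. If the same proportional shift is applied to both arms, and similar shares of each arm are imputed, the shifts largely cancel in the difference. The shift itself is not small: 10% of an MCS-12 of 40 is 4 points per imputed value. The contrast would nevertheless look stable, and that stability could be read as evidence against a kind of missingness that the check hardly probes.

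**Working it through.** **Yardstick.** Table 4 (final row) gives a detectable effect of 0.20–0.22 SD for N = 780. With d = (1.960 + 0.842) × √(4 × VIF/N), ICC 0 gives 2.802 × √(4/780) = 0.201. With ICC 0.02 and 80 programs, m = 780/80 = 9.75 and VIF = 1 + 8.75 × 0.02 = 1.175, so d = 0.2175, or 0.220 with t quantiles. The figure reproduces. It is a 6-month power figure and serves here only as a scale: 2.0–2.2 MCS-12 points at an assumed SD of 10.

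**Missing shares at 12 months.** A1 reports "N=733 (75% of attempted, RS: 364, CEP: 369) completed the survey", and A2 states: "The analytic sample for 6 months is comprised of 1,018 participants". Overall missingness is (1018 − 733)/1018 = 28.0%. The arm split of the 1,018 is not given. Baseline completers were RS 492 and CEP 489, which leaves 1018 − 981 = 37 clients unallocated.

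- Outer bounds: RS 492–529 and CEP 489–526, so missing shares are RS 26.0–31.2% and CEP 24.5–29.8%.
- Tighter bounds: A1 (3-year survey) lists 84 RS clients with no data at baseline, 6 or 12 months. A1's baseline dispositions put RS enrolment at 492 + 17 + 96 + 1 = 606. A4 describes the 1,018 as clients with any survey data, so RS is at most 606 − 84 = 522. The shares become RS 26.0–30.3% and CEP 25.6–29.8%.
- Near-even split (RS 504–510): about 27–29% in each arm.

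The ranges below use the outer bounds.

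**Assumptions not in the documents.** RS mean MCS-12 is 40 (range 35–45), CEP is 2 points higher, and the SD is 10 (range 8–12) with a normal distribution. All missing 12-month values are scaled, all 733 completers lie within the 1,018, and the few deaths are ignored. Simple arm means are used, without covariates.

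**MCS-12 mean.** With missing share f, mean μ and factor k, an arm mean moves by f(k − 1)μ. Take RS 504, CEP 514 and k = 0.9:

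- RS: −0.1 × 0.278 × 40 = −1.11
- CEP: −0.1 × 0.282 × 42 = −1.18
- Difference, same factor in both arms: −0.07
- Difference, CEP only: −1.18; RS only: 1.11 in the other direction
- Difference, CEP × 0.9 and RS × 1.1: −2.30

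Absolute movement of the difference at an RS mean of 40:

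| RS / CEP split | Common factor | CEP only | Opposite |
|---|---|---|---|
| 504 / 514 | 0.07 | 1.18 | 2.30 |
| 510 / 508 | 0.00 | 1.15 | 2.29 |
| 492 / 526 | 0.21 | 1.25 | 2.29 |
| 529 / 489 | 0.22 | 1.03 | 2.28 |

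Over means of 35–45 and all splits, a common factor moves the difference by at most 0.25, one arm only by 0.9–1.4, and opposite factors by 2.0–2.6. With equal arm means of 40 and 28% missing in each arm, opposite factors give 2 × 0.1 × 40 × 0.28 = 2.24.

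**MCS-12 ≤ 40.** The proportion in an arm is (1 − f)Φ((40 − μ)/σ) + fΦ((40/k − μ)/σ). With RS 510, RS mean 40 and SD 10, the CEP–RS difference in percentage points is:

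- no departure: −7.9
- both × 1.1: −7.5; both × 0.9: −8.0
- CEP only × 0.9: −3.1; RS only × 1.1: −3.9
- CEP × 0.9 with RS × 1.1: +0.9

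Over the grid, a common factor moves the difference by at most 1.9 points (0.9 with RS 510). One arm only moves it 2.7–6.6 points. Opposite factors reverse the assumed CEP advantage, to between +0.6 and +1.3.

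**Coverage at other waves.** At 36 months A2 analyses 980 clients, of whom 600 responded, so 380/980 = 38.8% are missing. At 6 months A1 gives 759 completers in total, so (1018 − 759)/1018 = 25.4% of the 1,018 are missing.

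**The case against.** The strongest reply is that the scaling is only half of the analysis. A4 places bootstrap imputations for unit nonresponse under the borrowing method, and A3 says item-level missingness was mostly below 5%. Unit nonresponse therefore dominates at 12 months, and the text leaves unclear which method governed MCS-12 values lost that way. Borrowing is not a uniform shift. Its effect depends on how the outcome varies across response-propensity cells, and because imputation is stratified by arm, that effect can differ by arm. This stands: the arithmetic above covers scaling only. It does not make borrowing a test of differential departure, however. Any difference between arms is incidental, and boundary cells are outside the stated rule.

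Several stronger readings are tempting but unsupported:

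- **That one factor was certainly used in both arms.** A4 does not say so. It is the natural reading of a text that names no arm, and no more.
- **That the check can show nothing.** With unequal missingness, and through the cut-off at 40, a common factor still moves the binary difference by up to about 1.9 points.
- **That borrowing moves every case by one cell.** A4 limits it to non-boundary cells.
- **That about 40% of each arm was imputed.** Dividing by enrolled clients gives 1 − 364/606 = 39.9% for RS and, with CEP enrolment of 489 + 19 + 131 + 1 = 640, 1 − 369/640 = 42.3% for CEP. The CEP-only shift would then be 0.1 × 40 × 0.423 = 1.7 points. A3 restricts follow-up imputation to the 1,018, so these figures include people who were never imputed.

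The plan also has alternative weights, a weighted 12-month endpoint analysis and raw-data comparisons. They are useful, but none specifies a non-ignorable departure.

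**Conclusion.** The point holds in a limited form. A4 states no arm-specific departure from missing at random. If one factor applies to both arms, the 10% scaling moves the MCS-12 difference by about 0.1 point, against 1.1–1.2 for the same departure in one arm and 2.2–2.3 for opposite departures. The last is about the size of the effect that the design could detect. Scaling is thus a weak test of the treatment contrast, though not an empty one. For borrowing, the finding is only that no arm-differential departure is specified.

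The sizes rest on the assumed MCS-12 means and SD and on the unreported arm split. Across the ranges tried, the ordering of the three scenarios does not change. None of this shows that the trial's results are biased; it shows that this check could not readily reveal it.

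**What to change.** 1. State the factor applied in each arm, and which method was used for MCS-12 values missing through unit nonresponse.
2. Add departures for RS only, CEP only and opposite directions, or a small tipping-point grid over the two arms, for MCS-12, MCS-12 ≤ 40 and PHQ ≥ 10.
3. Run the borrowing method by arm in the same way, and state what is done for boundary cells.
4. Apply these checks at 6 and 36 months as well as at 12.

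The imputations are already produced separately by arm, so the work is a few reruns of existing code. The downside is that some results may have to be reported as sensitive to missing data.

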Methods: Extension Study (Aims 1-3): Between 1/2014-10/2014, we approached 1004 CPIC clients initially screened as depressed from 89 programs and eligible for 3-year surveys; 600 participated (60%; RS 293, CEP 307). Aim 3: For client qualitative interviews, we approached 163 consecutive 3-year survey participants stratified by depression, race/ethnicity, gender and intervention; 104 participated (64%). For staff, we notified 289 completing 12 month surveys and used purposive follow-up stratified by community, service sector and intervention, to complete 51 interviews. Aim 4: We interviewed 49 county and community leaders planning HNI and 14 of 34 leaders attending a national briefing.

Data Sources: Self-report surveys (Aims 1 and 2) and semi-structured interviews (Aims 3 and 4).

Measures: Client outcomes are poor MHRQL ($MCS-12 \leq 40$) and depression ($PHQ-8 \geq 10$) (primary); PHRQL (12-item physical composite score (PCS-12), mental wellness, and behavioral-health hospitalization nights (community-prioritized); and use of outpatient services

(secondary). Clients and providers were asked about priorities for care and national stakeholders for responses to CPIC findings and related policy initiatives.

4-year follow-up of the 3-year sample (extension study).

The CPIC 4-year follow-up was added based on *community-stakeholder input that additional follow-up of the 3-year sample was desired to show longer-term effects on depression remission*. This follow-up built on the 3-year extension study as well as an opportunity to explore of using an existing funded cohort to recruit potential subjects into the Community and Patient Partnered Research Network (CPPRN).

Analyses plan: We will conduct 3-year end-status intent-to-treat analyses, and for 4-year follow-up of the 3-year sample, 4-year end status, with intervention status as the main independent variable, adjusted for baseline status and covariates, with response weights and multiple imputation (Aim 1); subanalyses of intervention effects within service sector at each follow-up (Aim 2); sensitivity analyses (raw data, longitudinal modeling and sector-by-intervention interactions); and thematic analyses of qualitative data (Aims 3 and 4)

7. Limitations

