We conducted a longitudinal sensitivity analysis using all waves of data (baseline, 6-months, 12-months, 3-years) without response weights, adjusting for baseline covariates as in the primary analysis. We specified a spline model, with a linear segment between baseline and the first follow-up for initial improvement and another linear segment for the subsequent follow-ups; the two linear segments were specified to join at the first follow-up. In analyzing continuously scaled PCS-12 as the dependent variable, we used a 3-level, mixed-effects regression model by using SAS PROC MIXED. To account for the intraclass correlation due to the multilevel structure, we specified random effects at the program level and a spatial power covariance

structure at the client level to account for unequal spacing of waves. Initial explorations of 3-level, random-effects logistic models using SAS PROC GLIMMIX for binary outcomes yielded unstable estimates for program-specific random effects. We utilized a generalized estimating equation (GEE) framework with logistic regression models for binary outcomes and Poisson models for counts using SAS PROC GENMOD, specifying exchangeable correlation at the program level. From the estimated spline models, we developed a contrast involving a linear combination of coefficients to test intervention effects at each end point (baseline, 6-months, 12-months, and 3-years) and tested differences between intervention groups in change from baseline to 6 months, 12 months, and 3 years.

Exploratory analyses. The CPIC study had 2 primary outcomes: poor MHRQL (12-item mental health composite score, MCS-12 \leq 40), and depressive symptoms (PHQ-8 \geq 10 or PHQ-2 $<$ 3 for 4-year follow-up); and a community-prioritized outcome of mental wellness (a response of at least “a good bit of the time” in the previous 4 weeks to feeling calm or peaceful, having energy, or being happy), based on community input matched to the 36-item short-form health survey quality-of-life items. We developed 2 indicators: “clinical remission” (PHQ-8 $<$ 10 or PHQ-2 $<$ 3) and, with stakeholder input, “community-defined remission” (PHQ-8 $<$ 10 or PHQ-2 $<$ 3 or MCS-12 $>$ 40 or any mental wellness). We also used a count of survey periods in remission from baseline up to 3-year follow-up. Intervention status was the client’s program assignment at enrollment to CEP or RS.

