For time (survey period) to first remission, we used Cox proportional hazard models for the full sample with any survey data (n = 1018), limited to those at risk for subsequent clinical (n = 995) and community-defined (n = 408) remission at baseline. We used linear regression for number of periods in remission during the course of 3 years for the full sample (n = 1018). We developed models including intervention status, adding social determinants, then depression treatment.⁵

Analyses for 4-year outcome:

We conducted intent-to-treat analyses with intervention status as the main independent variable, using logistic regression for probability of remission (clinical, community-defined) for the sample with 4-year data (n = 298). We conducted analyses parallel to the 3-year analyses noted previously, using the same covariates plus base-line measure of the outcome and the 1 baseline item differing by intervention status among 4-year completers.⁵

A5. References

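### Appendix A4 prints the same PHQ-2 rule for 4-year depressive symptoms and for remission, and its 4-year n of 298 conflicts with the 283 responders in Appendix A1

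*Combined protocol and SAP*

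**What the plan says.** **Outcome definitions.** Appendix A4 (Exploratory analyses) names two primary outcomes. Depressive symptoms is a PHQ-8 of 10 or more or, in the alternative, "PHQ-2 $<$ 3 for 4-year follow-up". The next sentence defines clinical remission as "PHQ-8 $<$ 10 or PHQ-2 $<$ 3" and repeats both cuts within the wider definition of community-defined remission.

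**Planned 4-year analyses.** Section 6 (Analyses plan) lists, under Aim 1, intent-to-treat analyses "for 4-year follow-up of the 3-year sample, 4-year end status, with intervention status as the main independent variable". The only 4-year model that Appendix A4 writes out is a logistic regression for the two kinds of remission, "for the sample with 4-year data (n = 298").

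**Responders.** Appendix A1 reports 598 clients attempted at 4 years (RS 292, CEP 306). It continues: "Of those, 283 (47.3%) participated (RS 143, CEP 140"). The remainder were 308 not reached, 1 deceased, 5 refused and 1 too ill.

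**Weights and imputation.** Appendix A2 describes the 4-year response weights as follows: "The weighting model to predict follow-up status from 3-year sample" uses a list of baseline and 3-year characteristics. For the 3-year analysis it gives the sample as all those attempted, "excluding 24 deceased cases (1,004 attempted - 24 deceased = 980"). On unit-level imputation, Appendix A3 says that "these procedures were applied in sequence for the baseline, 6-month, 12-month, and 3-year data". It does not mention the 4-year wave.

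**The concern.** An adverse outcome and a favourable outcome cannot share one threshold in one direction. The PHQ-8 cuts in Appendix A4 are complements (10 or more against below 10), but the PHQ-2 cuts are identical. No other section gives a PHQ-2 rule for depression. Section 6 gives only PHQ-8 of 10 or more, so the intended direction can be inferred but not confirmed from the documents. If depressive symptoms is analysed at 4 years, as Section 6 implies, and the rule is coded as printed, the result points the wrong way.

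The second problem is that the number analysed at 4 years differs from the number who responded. About half of those attempted were lost, so the response weights matter, and they depend on who is flagged as a responder. If the weights follow 283 responders and the outcome model uses 298 clients, the two do not describe the same people.

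**Working it through.** **1. PHQ-2 rule, applied as printed**

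| PHQ-2 score | Depressive symptoms (printed) | Clinical remission | Complement of remission |
|---|---|---|---|
| below 3 | yes | yes | no |
| 3 or more | no | no | yes |

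The printed symptom column equals the remission column in every row. This does not depend on the range of the scale. With the same covariates, weights and sample, a 4-year symptoms model coded this way has the same event as the clinical remission model. Its intervention odds ratio would therefore equal the remission odds ratio, where the intended result is the reciprocal, 1/OR.

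**2. Responder count in Appendix A1**

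The inputs are the 4-year disposition counts. The order is participated, not reached, deceased, refused, too ill.

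- RS: 143 + 143 + 1 + 5 + 0 = 292, as stated.
- CEP: 140 + 165 + 0 + 0 + 1 = 306, as stated.
- Total: 283 + 308 + 1 + 5 + 1 = 598, as stated.
- Response: 283/598 = 47.3%, as stated.

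The 283 is therefore reproduced in each arm, in total and as a percentage.

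**3. The same check with 298**

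- Total with the other counts fixed: 298 + 308 + 1 + 5 + 1 = 613, which is 15 more than the 598 attempted.
- Response: 298/598 = 49.8%, against the 47.3% stated.
- Difference: 298 − 283 = 15, and 15/283 = 5.3%.

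**4. Can a documented or plausible rule produce 298?**

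- The 3-year rule, attempted minus deceased (1,004 − 24 = 980), gives 598 − 1 = 597 at 4 years.
- Attempted minus not reached: 598 − 308 = 290. Removing the one death gives 289.
- Responders plus refusals: 283 + 5 = 288.
- Unit-level imputation is described only through the 3-year wave.

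None gives 298.

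**5. Size of the sample discrepancy**

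- Average inverse-response weight: 598/283 = 2.11 against 598/298 = 2.01.
- Ratio of standard errors, taking the standard error as proportional to 1/√n: √(298/283) = 1.026, or about 2.6%. This ignores clustering and unequal weights, so it is only a guide.

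**The case against.** **The intended direction is obvious.** The PHQ-8 pair in the same paragraph is complementary, and PHQ-2 below 3 appears twice for remission, so only one reading makes sense. This is a fair inference. But the contradictory line is the definition of a primary outcome, and nothing elsewhere confirms the correction.

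**The harm depends on an analysis that is not written out.** Appendix A4 specifies only remission at 4 years, and Section 6 says the wave was added to look at longer-term remission. Aim 1 itself names only the 3-year follow-up. Reversal needs a 4-year symptoms analysis to be run and the misprint to be carried into code, and the documents show neither. That stands, so the consequence is stated here only as conditional. However, the Section 6 analyses plan does place 4-year end status under Aim 1, whose primary outcomes include depression, and Appendix A4 refers to analyses parallel to those at 3 years.

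**The weights are already tied to the responders.** Appendix A2 models response to the 4-year survey, and Appendix A1 gives those responders as 283. That is right as far as it goes. What is missing is the link from that responder set to the 298 in the outcome model.

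**298 is probably a misprint.** It appears once, and Appendix A1 has other count slips. At 6 months, 759 completers are given against 380 + 359 = 739 by arm. At 3 years, both 1,004 and 1,014 are given as attempted, and 24 deaths against 14 + 11 = 25 by arm. A misprint is quite possible. The 4-year paragraph, unlike those, balances in every direction, which favours 283 but does not show which sample was analysed.

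**The average weights could use a base of 600.** The weighting model starts from the 3-year sample of 600, not the 598 attempted. The averages then become 600/283 = 2.12 and 600/298 = 2.01, which is immaterial.

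**Conclusion.** Both discrepancies are real, and neither is explained by the documents. The printed 4-year PHQ-2 rule for depressive symptoms is wrong as written, because it is identical to the remission rule. The specified remission models are unaffected. A 4-year symptoms model coded as printed would have its direction reversed. That the intended cut is PHQ-2 of 3 or more is an inference from the PHQ-8 pair.

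The 4-year n of 298 exceeds the reconciled responder count by 15 (5.3% of 283). The effect on precision is small. The consequence is that the 4-year remission result and the 4-year response weights cannot be tied to one defined set of clients. The documents do not settle whether 298 is a misprint or a different sample. The point should be corrected, but it does not show that any specified result is wrong.

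**What to change.** 1. In Appendix A4, state the 4-year depressive-symptoms rule as the complement of the remission rule (by inference, PHQ-2 of 3 or more), and confirm it against the analysis code.
2. In Appendix A4, reconcile the 4-year analysis n to the 283 responders, or say who the other 15 are and how they came to have 4-year data.
3. Check that the response indicator in the Appendix A2 weighting model flags the same clients as the outcome model.
4. Re-run the 4-year analyses only if the code used the wrong direction or the wrong sample.

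The cost is two one-line corrections to the appendix, plus a check of the outcome coding and the sample flag.
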